#### 4.3.2.2 Joint Status Assessment

The frequencies of pre-existing, new, resolved, EOS and change from baseline number of target joints per participant will be summarized as well as the median counts per participant. The change from baseline to EOS in the number of target joints will be summarized in a shift table.

#### 4.4.2 PK Parameters Derived from WAPPS-Hemo

The following WAPPS parameters will be summarized by risk score group and subgroup of history of FVIII inhibitors:

- Predicted post-infusion measurement of plasma factor activity level on Day 0 (Day of Infusion) up to Day 8,
- estimated terminal half-life, and
- time to 0.01, 0.02, 0.05, 0.1, and 0.2 IU/dL (with their credibility intervals),
- FVIII trough level (2 measures for participants with 2x/week regimen),
- area under the curve,
- clearance, and
- predicted peak factor value.

#### 4.4.3 Incremental Recovery and Trough Measurements of Jivi Levels

Actual sampling times before and after infusion and the dose administered will be presented in listings of FVIII levels. Incremental recovery FVIII levels will be presented with the corresponding participant weight value.

A summary of incremental recovery will be presented by risk group and also the frequency of samples failing validity criteria.

A summary of quantitative trough levels will be presented by risk group and also the frequency of trough levels above 1%, 3% and 5%.

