In this proposed clinical study, the effect of using a new risk score approach, based on the best known predictive phenotypic and biologic variables, to select the most appropriate prophylaxis regimen for reaching a favorable outcome will be assessed for participants switching from SHL to Jivi. The scoring approach in this study has not yet been validated and is different from classical risk-based models in that the score allocation and the dosing regimen itself has an influence on the outcome of interest. Due to the nature of the study, the inclusion of sub-populations such as mild/moderate hemophilia patients, women, and patients with past FVIII inhibitors should not prevent them from participating.

The scoring approach will be composed of 5 individually weighted variables: pre-study bleeding phenotype, previous treatment frequency, number of active target joints, von Willebrand factor (vWF) antigen levels, and physical activity. These variables were selected on the basis of the existing data regarding their established or potential role in determining the most appropriate EHL regimen.

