### **5. Study Population**

Previously-treated adolescent/adult ( $\geq 12$  years) patients with congenital hemophilia A on continuous prophylaxis with an SHL FVIII product for at least 6 consecutive months within the previous 12 months prior to the screening visit will be included. Medical records or a detailed participant documentation (i.e. diary, etc.) covering the last year is required to confirm the participant's prophylaxis treatment modality.

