### 8.1.3 Disease History

Specific information on history of hemophilia to be recorded at screening will include date of diagnosis, start of therapy, start of prophylaxis, for all prior and current FVIII products within 12 months, estimated number of EDs, type of FVIII gene mutation (from history, if available), family history, FVIII level and type of assay, family and personal history of past inhibitor formation (including date of inhibitor testing, whether immune tolerance induction was performed, and recovery and half-life data, if available; [Section 1.3](#)), previous or current SHL treatment product and regimen, used for score calculation, within 12 months of Baseline Visit, and number and type of bleeds derived from the before-mentioned SHL time period of a minimum of 6 months within the last 12 months of study screening . If available, data on prior PK with the participants' previous SHL FVIII product (used for score calculation) will be collected (concentration timepoints, and half-life).

Blood samples will be collected at screening to determine the participant's vWF antigen levels, if not already available in the medical records. If available in the medical records, vWF antigen testing should have been performed within 12 months prior to enrollment.

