### 1.1 Objectives and Endpoints

Objectives	Endpoints
Primary	
To assess the effect of using a baseline risk score, based on a participant's phenotypic and biologic variables, to select the most appropriate prophylaxis regimen for reaching a favorable outcome, when switching from a SHL product to Jivi	Occurrence of favorable outcome on the score selected dosing regimen
Secondary	
To assess the effectiveness of Jivi compared to a previous SHL treatment	ABR (total, joint, spontaneous) and change in total ABR from pre-study
To assess the frequency of Jivi administration	Change in the frequency of pre-study SHL treatment to the frequency of Jivi administration (infusions/month)
To assess the proportion of participants with 0 and $\leq 1$ spontaneous bleeds	Occurrence of participants with 0 and $\leq 1$ spontaneous bleeds
To assess participant quality of life (QoL) and physical activity, as measured by Patient Reported Outcomes (PROs)	Change in Haemophilia Quality of Life Questionnaire (Haem-A-QoL or Haemo-QoL KIDS, depending on age of participant); Patient's Global Impression of Change (PGI-C); EuroQoL 5 Dimensions (EQ-5D-5L) questionnaire; Treatment Satisfaction Questionnaire for Medication (TSQM); Work Productivity and Activity Impairment (WPAI) questionnaire scores
To assess target joint status, per International Society on Thrombosis and Haemostasis (ISTH) guidelines	Number of target joints and change in target joint status from baseline

Objectives	Endpoints
Other, Pre-specified	
To assess whether blood type and body mass index (BMI) would have led to a different score allocation	Participant score considering ABO type and BMI
To describe PK parameters derived from WAPPS-Hemo and assess any association with clinical risk score	PK parameters derived from WAPPS-Hemo
To determine participant Jivi trough levels while on a specific regimen	Trough measurement of Jivi levels
To determine the percentage of participants who can maintain > 1%, > 3 %, and > 5% FVIII trough levels while on a specific prophylaxis regimen	Occurrence of trough levels above 1%, 3% and 5%, stratified by prophylaxis regimen
Abbreviations: ABR = annualized bleeding rate; EQ-5D-5L = EuroQoL 5 dimensions; FVIII = human coagulation factor VIII; SHL = standard half-life	

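### SAP 4.4.3 counts FVIII troughs above 1%, 3% and 5% without regard to endogenous FVIII, although mild and moderate patients may enroll

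*SAP*

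**What the plan says.** **Population.** Protocol 2.1 says of certain groups: "the inclusion of sub-populations such as mild/moderate hemophilia patients, women, and patients with past FVIII inhibitors should not prevent them from participating". Protocol 5 describes "patients with congenital hemophilia A on continuous prophylaxis with an SHL FVIII product". Inclusion criterion 2 asks for congenital hemophilia A and at least 150 exposure days. Nothing in Protocol 5, 5.1 or 5.2 limits endogenous FVIII activity.

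**Objective and endpoint.** SAP 1.1 sets the objective as the "percentage of participants who can maintain > 1%, > 3 %, and > 5% FVIII trough levels" on a given regimen. The companion endpoint in the same table is labelled as a measurement of Jivi trough levels.

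**Analysis.** SAP 4.1.1.6 defines a trough as the FVIII level measured at Visit 6, plus Visit 5 for the twice-weekly regimen. SAP 4.4.3 then summarizes the levels and "the frequency of trough levels above 1%, 3% and 5" percent by risk group. It has no subtraction, restriction or severity split. The only subgroup in SAP 4.6.4 is inhibitor history.

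**Validity limits.** SAP 4.1.1.6 calls a trough invalid above 37.5% at day 3, 23.1% at day 4, 21.5 at days 5 and 6 (no unit printed; read here as %), and 8.1% at day 7 or later.

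**Data on endogenous FVIII.** Protocol 8.1.3 records "FVIII level and type of assay" at screening, and Protocol 8.5.2 has the baseline factor level entered in WAPPS-Hemo. SAP 4.6.2 summarizes the FVIII level at diagnosis as disease history. None of these is linked to the troughs.

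**The concern.** A one-time activity measurement is the sum of the participant's own FVIII and residual Jivi, and Protocol 8.5.1 describes no method to separate them. Where a participant's own level is already above a cut-off, being above it says nothing about the regimen. The SAP allows for pre-infusion FVIII elsewhere: incremental recovery in SAP 4.1.1.5 subtracts the pre-infusion level. The trough counts have no counterpart.

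What is at stake is how a sentence such as ‘x% maintained more than 3% on this regimen’ can be read. With 20 to 25 participants over three regimens, one or two people can move a regimen-level share visibly. If the regimens differ in severity mix, a comparison between them is confounded as well.

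**Working it through.** **The plan's own figure.** The documents give no expected value or precision for the trough shares. Their only sizing figure is the Clopper-Pearson interval for 14/20 with a favorable outcome (SAP 5). It reproduces as 45.7% to 88.1%, width 42.4 points, but it concerns the primary endpoint.

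**Step 1: which cut-offs are met automatically.** Let e be the endogenous level and r the residual Jivi, so the measured trough is e + r. Set r = 0, so that the regimen contributes nothing. The participant counts at cut-off c if e > c, and the trough is valid if e does not exceed the limit for that day. The values of e are chosen for illustration.

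| e | >1% | >3% | >5% | Validity under SAP 4.1.1.6 |
|---|---|---|---|---|
| 2% | yes | no | no | valid on every day |
| 3.5% | yes | yes | no | valid on every day |
| 6% | yes | yes | yes | valid on every day |
| 10% | yes | yes | yes | invalid at day 7 or later |
| 22% | yes | yes | yes | invalid from day 5 |
| 25% | yes | yes | yes | invalid from day 4 |
| 40% | yes | yes | yes | invalid on every day |

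The effect applies only to cut-offs below the participant's own level. At e = 2% the regimen must still supply more than 1 point for >3% and more than 3 points for >5%.

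**Step 2: effect on the reported share.** Among n participants with valid troughs, let k have e above the cut-off, and let s be the share above it in the rest. Then

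reported share = [k + (n − k)s]/n = s + m(1 − s), with m = k/n,

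and the excess over s is m(1 − s). Both k and s are assumptions. The excess, in percentage points, as s runs from 0.9 down to 0.3:

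| k | n = 20 | n = 25 |
|---|---|---|
| 0 | 0 | 0 |
| 1 | 0.5 to 3.5 | 0.4 to 2.8 |
| 3 | 1.5 to 10.5 | 1.2 to 8.4 |
| 5 | 2.5 to 17.5 | 2.0 to 14.0 |

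For example, n = 20, k = 3 and s = 0.5 give 0.5 + 0.15 × 0.5 = 57.5%. In one risk group of 8 (assumed size) with k = 2, 3/6 = 50% is reported as (2 + 3)/8 = 62.5%.

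**Step 3: what the validity limits do.** They leave levels of 1% to 5% untouched, so the >1% and >3% counts stay exposed. At day 7 or later they act on e + r. With e = 4%, any residual Jivi above 8.1 − 4 = 4.1 points makes the trough invalid, although there the regimen did carry the participant above 5%. SAP 4.1.1.6 does not say how invalid troughs are tabulated. The natural reading is that they are dropped, because SAP 4.1.1.5 removes invalid recovery values from its summaries. Dropping them is a second selection that depends on severity.

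**The case against.** The strongest reply is that the raw count answers a legitimate question. Protocol 2.1 describes one prophylaxis strategy as keeping FVIII activity above 1 IU/dL, which is total activity, and the objective is descriptive. On that reading the share is correct and misleads only if taken as Jivi's own contribution. This stands as a reason to keep the all-participant share. It does not remove the need for a second figure, since the objective ties the percentage to a regimen and the companion endpoint is labelled as Jivi levels.

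It is also fair that the number of such participants is unknown. Requiring 150 exposure days and stable prophylaxis may keep it small. SAP 4.6.2 shows FVIII level by risk group and SAP 4.1 lists all data, so a reader could see the severity mix, though not the share corrected for it.

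Three stronger readings are tempting, and the documents do not support them:

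- *That a mild or moderate participant counts as maintained whatever the regimen does.* This holds only for cut-offs below his own level and only with a valid trough.
- *That the inflation gathers in the low-risk, longest-interval group.* Neither severity nor endogenous FVIII is a score variable (SAP Table 1), the bleed variable is the rate while already on prophylaxis, and no section links severity to risk group. The validity limit is also tightest at day 7 or later, where a milder participant may be dropped and not counted.
- *That the WAPPS-Hemo outputs in SAP 4.4.2, "time to 0.01, 0.02, 0.05, 0.1, and 0.2", fail in the same way.* The baseline factor level is already an input (Protocol 8.5.2), SAP 1 puts those PK calculations outside its scope, and the documents do not say what the service returns for a threshold that is never reached.

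**Conclusion.** The point holds in a limited form. Mild and moderate patients may enroll, and the trough shares take no account of endogenous FVIII. Anyone whose own level exceeds a cut-off, with a trough inside the validity limits, counts as maintained at that cut-off whatever the regimen contributes. Automatic success at all three cut-offs needs an endogenous level above 5% and a measured trough within the limit for that day.

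Relative to the share among participants below the cut-off, the excess is m(1 − s). It is zero if no enrolled participant is above the cut-off, and the documents give no value for m. The figures above show scale and do not predict a result. That flagged troughs are dropped is an inference from SAP 4.1.1.5.

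Trough shares are an other pre-specified, descriptive endpoint, and the primary endpoint rests on bleeding rate and infusion frequency. This is a low-priority improvement.

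**What to change.** - **SAP 4.4.3:** keep the all-participant share. For each cut-off, also report by regimen the share among participants whose documented endogenous FVIII is below that cut-off, and list the others separately. Base any statement about what a regimen maintains on the restricted share.
- **SAP 4.1.1.6:** state that the upper validity limits are not applied unadjusted to participants with measurable endogenous FVIII. State whether invalid troughs leave the frequency table, and report how many are excluded.

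The cost is SAP wording and one extra table, from data already collected. Denominators become smaller and differ between cut-offs. The split also relies on a historical FVIII value, perhaps from diagnosis and another assay. A participant just below a cut-off stays in the restricted set with his own FVIII still contributing, so the correction is partial. If no enrolled participant is endogenously above a cut-off, the two shares coincide.

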### 4.5 Safety Analyses

All safety analyses will be performed on the safety analysis set. Summary tables will be presented overall and stratified by subgroup of history of FVIII inhibitors.

#### 4.5.1 Extent of Exposure

Intervention period as defined in [section 4.1.1.1](#), and total dose (in IU/kg) summarized across eDiary entries will be summarized for the safety analysis set by risk group and overall. Total dose will also be presented for the intervals of month 1, month 2, and  $\geq 3$  months from Day 1 (Day 1 through Day 30, Day 31 through Day 61, Day 62 until censoring, and Day 62 until EOS.

#### 4.5.2 Adverse Events

Adverse events will be reported using the latest version of the Medical Dictionary for Regulatory Affairs (MedDRA).

All AEs, SAEs, and AESIs will be collected from Baseline until the end of the Safety Follow-up Visit at the time points specified in the protocol schedule of activities (SoA). Only (S)AEs which are related to protocol-required study procedures will be recorded from the signing of the consent form until the start of study intervention. Adverse events or SAEs will be considered to be treatment-emergent (TEAEs or TE SAEs) if they have started or worsened after first administration of study intervention and not later than 7 days after the last infusion of Jivi.

The AE assessments recorded on the eCRF include SAE (yes/no) and SAE criteria, AESI (yes/no), reasonable causal relationship to Jivi (yes/no), reasonable causal relationship to protocol-required procedure (yes/no), medical device AE or deficiency (yes/no), intensity (mild/ moderate/ severe), action taken with the study intervention (drug withdrawn/ drug interrupted/ dose reduced/ dose not changed/ dose increased/ not applicable/ unknown), remedial drug therapy (yes/no), other actions or treatments of AE, and outcome. The AESIs are hypersensitivity and loss of efficacy (LoE).

An overall summary table of TEAEs will be presented to include all participants and stratified by subgroup of history of FVIII inhibitors. The Overall summary will include number and percentage of participants experiencing AEs in the following categories:

- Any TEAE
- Any TEAE by maximum intensity
- Any study intervention-related TEAE
- Any study procedure-related TEAE
- Any medical device-related TEAE
- Any medical device deficiency
- Any TEAE leading to discontinuation of the study intervention
- Any TEAE of Special Interest (TE AESI), including SAE/AE
- Any study intervention-related TE AESI, including SAE/AE
- Any TE SAE
- Any study intervention-related TE SAE
- Any study procedure-related TE SAE
- Any medical device-related SAE
- Any TE SAE leading to discontinuation of study intervention
- Any TEAE with outcome death

An overall summary of pre-treatment AEs will include number and percentage of participants experiencing pre-treatment AEs in the following categories:

- Any AE with causal relationship to protocol-required study procedures
- Any SAE with causal relationship to protocol-required study procedures
- Any AE with causal relationship to protocol-required study procedures with outcome death

If post-treatment AEs occur (i.e., those occurring >7 days after the last infusion of Jivi), these will be presented in an overall summary table and in a summary by primary SOC and PT.

In all AE summary tables, multiple AEs within same category of primary system organ class (SOC) or preferred term (PT) for a participant will be counted only once in that category. In summaries of events with causal relationship a participant with related and unrelated events in any category will be counted for event with causal relationship experienced in that category.

The following summaries of TEAEs will be presented

- TEAEs by primary SOC and PT overall and stratified by FVIII inhibitor history

The following summaries of TEAEs will be presented overall

- Study intervention-related TEAEs by primary SOC and PT
- Study intervention-related TE AESIs (including SAE/AESI) by primary SOC and PT
- Study procedure-related TE AESIs (including SAE/AESI) by primary SOC and PT
- Medical device-related TE AE by primary SOC and PT
- Medical device deficiency
- TEAEs leading to discontinuation of the study intervention by primary SOC and PT
- TE non-serious AEs by primary SOC and PT

The following summaries of TE SAEs will be presented

- TE SAEs by primary SOC and PT
- Study intervention-related TE SAEs by primary SOC and PT
- Study procedure-related TE SAE AESIs by primary SOC and PT
- Medical device-related TE SAE by primary SOC and PT

Individual listings of AEs, SAEs, and AEs leading to discontinuation will be provided with a flag to identify TE status. The individual listings will include any information on history of FVIII inhibitors.

If any death occurs, then summaries and listings of fatal AEs and deaths will be provided.

#### 4.5.3 Additional Safety Assessments

- The record of pregnancy test performed will be summarized by visit.

Details of all pregnancies in female participants will be collected after the start of study intervention and until 8 weeks after last dose of study intervention.

While the pregnancy itself is not considered to be an AE or SAE, any pregnancy complication or elective termination of a pregnancy for medical reasons will be reported as an AE or SAE.

- Number and percentage of participants with confirmed positive FVIII inhibitor titer classified low ( $\geq 0.6$  BU/mL and  $\leq 5$  BU/mL) or high (based upon persistence of an inhibitor  $> 5$  BU) will be presented for the safety analysis set.
- Screening hematology assessments will be presented for the safety analysis set. In case of multiple assessments were performed for one participant, the summary will include the latest assessment prior to Day 1. A grouped summary of platelet count will be presented: Platelet count  $< 100,000/\text{mm}^3$  and  $\geq 100,000/\text{mm}^3$ .

- Number and percentage of participants with abnormal hematology during the study intervention period will be presented for the safety analysis set.
- Vital signs at baseline and Visit 6/ EOS will be presented for safety analysis set. In case of repeat baseline assessments performed for one participant, the summary will include the latest assessment prior to Day 1.

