## 1.3 Schedule of Activities (SoA)

Procedure	Visit 1 (Screening)	Intervention Period Months						Notes
		Visit 2 a (Baseline)	Visit 3	Visit 4	Visit 5 a	Visit 6 a (EOS/Early Withdrawal) b	Visit 7 (Safety Follow-up)	
		Up to 30 days before Day 1	Day 1	Month 1 (±7 days)	Month 2 (±7 days)	Month 3 (±7 days)	Month 6 (+14 days)	7 to 14 days after last dose
Contact	Visit	Visit	Phone	Phone	Visit	Visit	Phone	
Informed consent/assent	X							
Inclusion and exclusion criteria	X	X						Recheck clinical status before first dose of study medication.
Demography	X							
Weight	X				X			
Physical examination including height, weight		X				X		
Joint status (defined by ISTH)		X				X		
Highly sensitive serum pregnancy test (WOCBP only)	X	X c			X	X		
Physical activity level (contact/no contact/sedentary)		X d			X	X		
History of hemophilia	X							
Previous hemophilia treatment	X							
Other past and current medical conditions and surgical history (includes substance usage)	X							Substances: drugs
Total risk score calculation		X						
PROs e		X			X f	X		
FVIII levels: pre-dose, 15-30 minutes post-infusion, and at a minimum of 4 hours post-infusion		X g			X g	X g		A 3- or 5-day wash-out period is required for those patients whose previous product was an SHL or EHL, respectively
WAPPS-Hemo analysis					X h	X g, h		FVIII levels to be used from Visit 2 (if felt to be accurate levels) and Visit 5 (72-hour post-infusion level). See footnote h

Procedure	Visit 1 (Screening)	Intervention Period Months						Notes
		Visit 2 a (Baseline)	Visit 3	Visit 4	Visit 5 a	Visit 6 a (EOS/Early Withdrawal) b	Visit 7 (Safety Follow-up)	
		Up to 30 days before Day 1	Day 1	Month 1 (±7 days)	Month 2 (±7 days)	Month 3 (±7 days)	Month 6 (+14 days)	7 to 14 days after last dose
Laboratory assessments (hematology: CBC)	X							
Immunogenicity (FVIII inhibitor)	X							If suspect inhibitor to follow local clinical guidance for inhibitor testing
History of previous FVIII inhibitor	X							Please refer to eligibility criteria ( Section 5.1 and 5.2 ) for participants with a history of inhibitors. Recovery and half-life data for the SHL product should be extracted from medical records when available.

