## 2.3 Benefit/Risk Assessment

Jivi has received marketing authorization by the Food and Drug Administration (FDA), European Medicines Agency (EMA), Pharmaceutical and Medical Devices Agency (PMDA), Health Canada and other regions of the world for the treatment and prevention of bleeds in patients  $\geq 12$  years of age.

Jivi has demonstrated the potential for dosing Q5D or Q7D in a majority of participants in clinical studies, offering the option of a prophylaxis treatment with less frequent dosing for hemophilia A patients  $\geq 12$  years of age. For patients with increased bleeding tendency, 2x/week treatment with Jivi provided an efficacious treatment option.

The potential benefits to participants are less frequent dosing and less reliance on central venous catheters, which may reduce physical and emotional burden for the participant, leading to better adherence. This, in turn, may translate into improved FVIII activity, good activity coverage, and good prophylactic coverage from bleeds.

As with all FVIII replacement therapies, the most serious expected adverse event (AE) is the development of inhibitory antibodies against FVIII rendering FVIII treatments ineffective. No new or confirmed inhibitors have been observed during the clinical studies. Other known risks for the class of FVIII replacement products are allergic type of hypersensitivity reactions which may progress to anaphylaxis (including shock), cardiovascular events, and possible catheter-related complications. Data from more than 200 patients aged 2 to 62 years demonstrated that these risks are not different for Jivi administered to PTPs. No cases of anaphylaxis were reported, and no serious cardiovascular event was observed.

A clinical immune response associated with anti-PEG antibodies, manifested as symptoms of acute hypersensitivity and/or loss of drug effect has been observed within the first 4 exposure days (EDs) primarily in children  $< 6$  years of age (Study 15912 – PROTECT VIII Kids). Low post-infusion FVIII levels in the absence of detectable FVIII inhibitors indicate that loss of drug effect is likely due to anti-PEG IgM antibodies; in such cases Jivi should be discontinued and patients switched to a previously effective FVIII product.

More detailed information about the known risks and reasonably expected AEs of Jivi may be found in the approved prescribing information.

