### 8.3.1 Measurements of Immunogenicity

All participants will be tested for inhibitors to FVIII according to the Bethesda assay as per local clinical practice. A positive inhibitor test is defined with a threshold of  $\geq 0.6$  BU/mL. Repeat testing should be obtained within 1 to 2 weeks of initial identification of a positive result. Only after confirmation of a second positive result does the inhibitor have to be reported as a SAE.

A low post-infusion FVIII level in the absence of detectable FVIII inhibitors indicates that loss of drug effect is likely due to anti-PEG antibodies. Jivi should be discontinued and participants switched to a previously effective FVIII product (refer to [Section 8.4.7](#) as this qualifies for an AESI-Loss of Efficacy [LoE]).

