##### **9.4.4.1 Immunogenicity**

Inhibitor development will be summarized by time point and presented in participant listings. The purpose of the listing is to delineate the clinical factors which may be positively associated with development of the inhibitor. Confirmation of positive inhibitor titers (Bethesda assay, as per local clinical practice,  $\geq 0.6$  BU/mL) will require repeat measurement. If the repeated inhibitor result is  $< 0.6$  BU without intervention, the inhibitor is not confirmed and should not be reported as an SAE. Inhibitors will be classified as being either low titer ( $\geq 0.6$  BU/mL and  $\leq 5$  BU/mL) or high titer based upon persistence of an inhibitor  $> 5$  BU.

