Note: If available in the medical records, vWF antigen testing should have been performed within 12 months prior to enrollment
  - HIV screening, if not available in medical records

- CD 4+ cell count (only if participant is HIV positive and if not available in medical records)
- Immunogenicity testing (human recombinant factor VIII [rFVIII] inhibitor)
- Training on use of eDiary and confirm participant access to eDiary

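### FVIII inhibitor testing is scheduled only at screening, yet the SAP reports on-study inhibitors as a percentage of all treated participants without showing how many were tested

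*SAP*

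**What the plan says.** Protocol section 2.3 states that for this drug class "the most serious expected adverse event (AE) is the development of inhibitory antibodies against FVIII rendering FVIII treatments ineffective". Section 7.1.1 makes any confirmed titer of 0.6 BU/mL or more an SAE.

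The Schedule of Activities (section 1.3) marks the inhibitor row at Visit 1 only, with the note "If suspect inhibitor to follow local clinical guidance for inhibitor testing". Appendix 7 agrees: section 11.7.1 lists "Immunogenicity testing (human recombinant factor VIII [rFVIII] inhibitor") among the screening samples, section 11.7.2 requires a negative result before the first dose, and sections 11.7.3 to 11.7.6 list no inhibitor test at Visits 3 to 7. The one on-study inhibitor sample that the protocol spells out belongs to the loss-of-efficacy work-up in section 8.4.7.

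On analysis, protocol section 9.4.4.1 says "Inhibitor development will be summarized by time point and presented in participant listings". SAP section 4.5.3 plans the "Number and percentage of participants with confirmed positive FVIII inhibitor titer classified low" (0.6 to 5 BU/mL) or high (persistently above 5 BU), for the safety analysis set, which SAP Table 3 defines as everyone with at least one dose.

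The same SAP section plans two neighbouring displays. One concerns blood counts: "Number and percentage of participants with abnormal hematology during the study intervention period will be presented for the safety analysis set". The other is a two-visit display of a different measurement, for which the SAP says: "Vital signs at baseline and Visit 6/ EOS will be presented for safety analysis set".

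**The concern.** A percentage invites the reader to take its denominator as the people in whom the event could have been found. Here the denominator is everyone treated, while a numerator event needs someone to have ordered a test. If no inhibitor is reported, the table shows 0 of N, and nothing in SAP section 4.5.3 tells the reader whether N participants were tested on Jivi or only a few. The statement concerns the risk that the protocol itself ranks first, in a study that admits participants with a past inhibitor (Inclusion Criterion 5).

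Separately, an analysis by time point needs more than one time point, and the schedule gives only the one before dosing.

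**Working it through.** **Step 1. Is the SAP percentage an on-study rate?** Exclusion Criterion 3 rules out an inhibitor in the year before entry, and section 11.7.2 requires a negative result before dosing. Any confirmed positive in the safety set must therefore arise after the first dose. The screening test adds nothing to the numerator.

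**Step 2. How many post-baseline tests are scheduled?** None at Visits 3 to 7. Post-baseline results exist only if a test was prompted. It follows that the summary by time point in section 9.4.4.1 cannot be produced from scheduled data. The SAP does not carry the phrase over, although its sections 1 and 4.7 declare no change to the protocol's analyses.

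**Step 3. Does any SAP rule reveal the number tested?** SAP section 4.1 promises counts of available and missing values for metric data. Inhibitor status is categorical, so that promise does not reach it. The general rule is that missing clinical outcomes are not imputed. Section 4.5.3 gives no number tested.

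**Step 4. Illustration of what is hidden.** The documents state no inhibitor rate and plan no interval for it, so there is no figure to reproduce. As a check of method, the exact Clopper-Pearson interval for 14/20 gives 45.7% to 88.1% (width 42.4) and for 17/25 gives 46.5% to 85.1%, both as in SAP Table 4.

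For zero events the two-sided 95% upper limit is 1 − 0.025^(1/n):

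| Result | Basis | Upper limit |
|---|---|---|
| 0/25 | whole safety set | 13.7% |
| 0/20 | whole safety set | 16.8% |
| 0/10 | 10 tested (assumed) | 30.8% |
| 0/5 | 5 tested (assumed) | 52.2% |

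The last two rows treat those tested as a random sample. Under testing on suspicion they are not, so the rows show only how much the missing count could matter.

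**Step 5. Chance of seeing any case.** Assume a true rate of 5%, with a random quarter of cases detected. The chance of at least one detected case is 1 − (1 − 0.05 × 0.25)^N, which is 22% for N = 20 and 27% for N = 25. With everyone tested it is 1 − 0.95^N, or 64% and 72%. Both the rate and the quarter are assumptions.

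**Step 6. Would a tested-only percentage be better?** With one case and 5 of 25 tested, the safety-set figure is 1/25 = 4% and the tested-only figure 1/5 = 20%. If those 5 were tested because an inhibitor was suspected, 20% overstates the rate in the treated population. The 4% may understate it. Neither works alone.

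**Step 7. Neighbouring items in SAP section 4.5.3.** The complete blood count is scheduled at Visit 1 only, so the on-study abnormal-hematology percentage has the same missing denominator. Vital signs are collected only after an infusion-related AE at a site visit (Schedule of Activities, footnote m), so a routine baseline and end-of-study presentation has no scheduled data behind it.

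**The case against.** **Detection is not absent.** The Schedule of Activities note and the loss-of-efficacy work-up provide for-cause tests, and FVIII levels are measured in everyone at Months 3 and 6, which could raise suspicion. Clinically evident inhibitors would probably be found. This stands, and it confines the point to silent or low-titer inhibitors. It does not remove it: low titer is one of the SAP's two reporting classes, and routine recovery is measured only at the first infusion, repeated only if those levels look wrong.

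**A reader might infer that the SAP counts untested participants as inhibitor-free.** No section says so. The general rule is no imputation, and the table shells are in a separate document that may print the number tested. What the text supports is that the default denominator permits that misreading.

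**A reader might see protocol section 8.3.1 as a second contradiction**, since "All participants will be tested for inhibitors to FVIII according to the Bethesda assay as per local clinical practice". It gives no time, so the screening test satisfies it. The mismatch lies in section 9.4.4.1.

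**A reader might expect testing to be more frequent in those with an inhibitor history, biasing that comparison.** Nothing in the documents says this, and the subgroup is shown only if each group has at least 5 participants.

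**A reader might take the vital-sign item as a planned abnormality percentage.** The SAP plans only a presentation. For such metric data it counts missing values, so the gap would be visible.

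**Context.** This is a Phase 4 study of an approved product in patients with at least 150 exposure days, with no new or confirmed inhibitors in earlier studies and no safety objective in section 3. For-cause testing is a disclosed choice. That argues against treating the matter as critical, not against showing the number tested.

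**Conclusion.** The point holds as one of reporting and consistency. The SAP percentage is an on-study rate with no scheduled test behind it, section 4.5.3 does not plan to show how many were tested, and the by-time-point summary in protocol section 9.4.4.1 cannot be delivered. The on-study hematology percentage shares the defect, and the vital-sign presentation conflicts with footnote m.

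The size is unknown, because the number tested on study is not in the documents. The limits in the working rest on assumed numbers tested and on intervals that the SAP does not plan, so they should not be quoted as findings. If everyone happened to be tested, the two denominators would agree. No efficacy endpoint is affected. This should be fixed, but it does not threaten the study's main result.

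**What to change.** **SAP section 4.5.3, inhibitors.** Keep the count over the safety set and label it *clinically detected (for-cause) inhibitors*. Beside it print the number with and without a post-baseline inhibitor result, overall and, if that subgroup is shown, by inhibitor history. Do not describe the safety-set percentage as incidence. Do not use a tested-only percentage as the sole rate, because testing on suspicion selects likely positives.

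**Protocol section 9.4.4.1.** Reconcile it with the Schedule of Activities by deleting the reference to time points and stating that on-study ascertainment was for cause, unless the sponsor chooses to schedule a post-baseline test. Scheduling one is optional; it would be a protocol change needing IRB approval, and samples from visits already completed may be out of reach.

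**SAP section 4.5.3, neighbouring items.** Show the number assessed beside the on-study hematology percentage, or delete it. Reconcile the baseline and end-of-study vital-sign presentation with footnote m.

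**Cost.** Without the optional test, this is wording and table shells only. The downside is that the safety statement reads slightly less favourably.
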